## 8 STATISTICAL CONSIDERATIONS

### 8.1 Sample Size Determination

A sample size of 150 subjects (75 subjects per treatment group) is planned based on the primary comparison of the proportion of subjects with IMACS DOI (as defined under the primary objective) at Day 169 (Week 24) between the SC abatacept group and the placebo group on a background of standard treatment.

A sample size of 150 subjects randomized in a 1:1 ratio to the SC abatacept group and placebo group will yield a power of approximately 90% to detect a treatment difference of 27% in the rate of IMACS DOI between the 2 treatment groups based on a continuity corrected chi-squared test. This power estimate assumes a two-sided alpha level of 5%, IMACS DOI rate of 60% in the abatacept group and 33% in the placebo group.

The 60% estimate of IMACS DOI in the abatacept group was based on reported rates of IMACS DOI in studies of patients with Myositis on combination therapy with another biologic agent. It is expected that the rate of IMACS DOI on abatacept in combination with standard treatment should be similar to that observed with the use of another biologic agent in combination with standard treatment. Table 8.1-1 below presents the power estimates for other considerations of proportion of subjects in IMAC DOI in the abatacept group assuming the total sample size of 150 subjects. Randomization will be stratified globally by 3 stratification variables: (1) disease diagnosis (Dermatomyositis [DM] vs non-DM IIM), (2) Interstitial Lung Disease (ILD) (present vs absent), (3) Japan vs ROW.

Table 8.1-1: Estimates of Power for Various Assumed Rates of IMACS DOI at Week 24 Assuming Total Sample Size of 150			
Aba Rate	Placebo Rate	Delta	Power (%)
50%	20%	30%	96
	25%	25%	85
55%	25%	30%	95
	30%	25%	84
60%	25%	35%	~ 99
	30%	30%	95
	35%	25%	83

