7.1 General Methods

The table below provides an overview of the efficacy analyses to be performed. These are thought to be robust in the case of the small marginal strata (Japan) frequencies of 20 or more (10 per treatment group); otherwise, some strata may be dropped from the models.

Table 7.1-1: Planned Efficacy Analyses

Measure of Interest	Analysis Method
IMACS DOI at Day 169 (Week 24)	
Primary Analysis:
 Using a logistic regression model that includes treatment group, stratification factors: disease diagnosis (DM vs. Non-DM), ILD (absent vs. present), Region (Japan vs. ROW), baseline MMT8 score, baseline MDAAT, and baseline PGA. Point estimate of adjusted ORs, corresponding 95% CI and p-value will be provided. The proportion of subjects in IMACS DOI in each treatment group and corresponding 95% CI will also be provided.
Time to event (IMACS DOI at 2 consecutive time points) up to Day 169 (Weeks 12 and 24)	Point estimates and 95% CIs for the hazard ratio of abatacept versus placebo will be based on Cox proportional hazards models. The stratification factors: disease diagnosis (DM vs. Non-DM), ILD (absent vs. present), Region (Japan vs. ROW), baseline MMT8 score, baseline MDAAT and baseline PGA will be included in the model. Observations from subjects who discontinue due to lost to follow-up will be censored at the date of last available data in the study. The date of the first IMACS DOI of the 2 consecutive IMACS DOI events will be used in the analysis. Estimate the distribution of time to first occurrence of event using Kaplan-Meier method/curve.
Changes from baseline in continuous variables (i.e., FI-2 scores, MRC total improvement score, IMACS core components, XXXXXXXXXX)	Longitudinal (repeated measures) model [including treatment group, baseline value of variable and randomization stratification factors: disease diagnosis (DM vs. Non-DM), ILD (absent vs. present), Region (Japan vs. ROW), time (categorical as study visit at which variable was measured), time by baseline value of variable and time by treatment as fixed effects and subject as a random effect], adjusted mean, SE, 95% CI for adjusted mean difference between treatment groups will be provided for all time

Table 7.1-1: Planned Efficacy Analyses

Measure of Interest	Analysis Method
	points. In addition, nominal p-values will be provided for the secondary endpoints of change from baseline at Day 169 (week 24) analysis.

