7.5.1 Hierarchical Testing for Primary and Key Secondary Endpoints

If the test for the primary endpoint (proportion of subjects who achieved IMACS DOI at Day 169) is statistically significant at a level of 5%, then a hierarchical approach for statistical testing will be used for the secondary endpoints. Hierarchical ordering of the secondary endpoints is as follows:

- Mean change from baseline in HAQ-DI at Day 169.
- MRC total improvement score at Day 169.
- Mean change from baseline in muscle endurance using FI-2 at Day 169.
- Mean change from baseline in MDAAT, based on the extramuscular disease activity VAS, at Day 169.

P-values will be presented for each of these endpoints. However, endpoints should not be interpreted for significance if they have a rank lower than that endpoint whose null hypothesis was the first that could not be rejected. That is, the significance of endpoints should not be interpreted if they have a rank lower than that endpoint whose test was the first to be non-statistically significant (p-value > 0.05).

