7.5.2 Primary Efficacy Analysis

The primary comparison of proportion of subjects in IMACS DOI at Week 24 between the SC abatacept and placebo groups will be assessed using a logistic regression model. To account for randomization stratification, the logistic regression model will adjust for the randomization stratification variables of disease diagnosis (DM vs. Non-DM), Interstitial Lung disease status (present vs. absent), and Japan vs. ROW; baseline MMT8 score, baseline MDAAT, baseline PGA and treatment group will also be included in the model. Point estimates of the adjusted Odds Ratios (OR) of the odds of achieving IMACS DOI in the abatacept group compared to the placebo group, corresponding 95% CI and p-value will be provided. Point estimates of the proportion of subjects in IMACS DOI in each treatment group and corresponding 95% CI will also be provided. All subjects who discontinue study medication prematurely prior to reaching the Week 24 assessment visit and/or received rescued medication at any time during the 24 week double-blind period, will be considered as not achieving IMACS DOI for the primary analysis. Efficacy assessments collected at Week 24 on subjects who discontinue study medication prior to Week 24 will not be included in the primary analysis of the primary endpoint, but will be included in a sensitivity analysis of the primary endpoint. Details of imputation rules for classification of IMACS DOI response for subjects with missing components of IMACS are provided in [Section 8.1.9](#). A table summarizing the number of imputed values for the primary endpoint by treatment group and missing data pattern will be provided. A summary of number of missing IMACS core measure item by treatment group will also be provided for subjects whose IMACS data are missing at Week 24 because of missing component data.

The primary estimand of the treatment difference in the proportion of subjects with IMACS DOI at Day 169 is the odds ratio (abatacept versus placebo) in the ITT analysis population that would be observed if all subjects who prematurely discontinued or received rescue medication before Day 169 or had missing IMACS DOI data would be non-responders.

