7.5.4 Secondary Efficacy Analysis

In addition to the primary efficacy endpoint, analyses related to the secondary [REDACTED] [REDACTED] will also be included in the Week 24 analysis. The secondary efficacy assessment of change from baseline in muscle endurance using FI-2 up to Day 169 (Week 24) will be assessed using a longitudinal (repeated measures) model including treatment group, baseline FI-2 value and randomization stratification factors: diagnosis (DM vs. Non-DM), ILD, Japan vs. ROW, time (categorical as study visit at which FI-2 is measured), time by baseline FI-2 and time by treatment interactions as fixed effects and subject as a random effect. Adjusted mean, SE, 95% CI for adjusted mean difference between treatment groups by study visit will be provided.

A similar longitudinal model will also be used to assess the change from baseline in HAQ-DI up to Day 169 (Week 24). The model will include treatment group, baseline value HAQ-DI value, randomization stratification factors: disease diagnosis (DM vs. Non-DM), ILD, Region (Japan vs. ROW), time (categorical as study visit at which HAQ-DI is measured), time by baseline HAQ-DI and time by treatment interactions as fixed effects and subject as a random effect. Adjusted mean, SE, 95% CI for adjusted mean difference between treatment group by study visit will also be provided.

The secondary efficacy assessment of change from baseline in extra-muscular disease activity MDAAT value will also be assessed using a longitudinal (repeated measures) model including treatment group, baseline value extra-muscular disease activity MDAAT value, randomization stratification factors: disease diagnosis (DM vs. Non-DM), ILD, Region (Japan vs. ROW), time (categorical as study visit at which extra-muscular disease activity MDAAT is measured), time by baseline extra-muscular disease activity MDAAT and time by treatment interactions as fixed effects and subject as a random effect. Adjusted mean, SE, 95% CI for adjusted mean difference between treatment groups by study visit will also be provided.

A similar longitudinal model will also be used to assess the Myositis Response Criteria (MRC) total improvement score up to Day 169 (Week 24). The mixed model will include treatment group and randomization stratification factors: disease diagnosis (DM vs. Non-DM), ILD (absent vs. present), Region (Japan vs. ROW), time (categorical as study visit at which MRC is measured)

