APPENDIX 2 MYOSITIS RESPONSE CRITERIA

The final myositis response criteria for minimal, moderate and major improvement in adult dermatomyositis/ polymyositis (DM/PM) and combined DM/PM and juvenile DM clinical trials and studies.

Table 10-2: Myositis Response Criteria

Core set measure, level of improvement based on absolute percent change	Improvement score
Physician global activity	
Worsening to 5% improvement	0
>5% to 15% improvement	7.5
>15% to 25% improvement	15
>25% to 40% improvement	17.5
>40% improvement	20
Patient global activity	
Worsening to 5% improvement	0
>5% to 15% improvement	2.5
>15% to 25% improvement	5
>25% to 40% improvement	7.5
>40% improvement	10
Manual muscle testing	
Worsening to 2% improvement	0
>2% to 10% improvement	10
>10% to 20% improvement	20
>20% to 30% improvement	27.5
>30% improvement	32.5
Health Assessment Questionnaire	
Worsening to 5% improvement	0
>5% to 15% improvement	5
>15% to 25% improvement	7.5
>25% to 40% improvement	7.5
>40% improvement	10
Enzyme (most abnormal)	
Worsening to 5% improvement	0
>5% to 15% improvement	2.5
>15% to 25% improvement	5
>25% to 40% improvement	7.5
>40% improvement	7.5
Extramuscular activity	
Worsening to 5% improvement	0
>5% to 15% improvement	7.5
>15% to 25% improvement	12.5
>25% to 40% improvement	15
>40% improvement	20

The total improvement score is the sum of all 6 improvement scores associated with the change in each core set measure. A total improvement score of ≥ 20 represents minimal improvement, a score of ≥ 40 represents moderate improvement, and a score of ≥ 60 represents major improvement. If one of the core measures is missing then the total score will be missing.

Improvement Score Calculation

The absolute percent change $((\text{post-baseline value} - \text{baseline value}) / \text{range}) * 100$ is calculated for each core set measure. For muscle enzymes, the most abnormal serum muscle enzyme level at baseline (creatinine kinase, aldolase, alanine transaminase, aspartate aminotransferase, lactate dehydrogenase) is used.

The range for each of the core set measures are as follows:

Muscle Enzymes: The enzyme range was calculated based on a 90% range of enzymes from natural history data as follows:

Creatinine Kinase: Range = 15 times the upper limit of normal (ULN)

Aldolase: Range = 6 times the ULN

Lactate dehydrogenase, aspartate aminotransferase, and alanine transaminase: Range = 3 times the ULN.

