The ULN is based on what is reported in the lab dataset for each enzyme.

Ranges for other core set measures:

Physician Global Assessment of Disease Activity (PGA) VAS: Range = 10

Patient Global Assessment of Disease Activity (SGA) VAS: Range = 10

Manual Muscle Testing (MMT-8): Range = 150

HAQ: Range = 3

Extramuscular Global Activity (using MDAAT): Range = 10

An improvement score is assigned for each core set measure based on the absolute percent change in the core set measure according to the definition in Table 2.1 above. These individual core set measure improvement scores are then totaled among the 6 core set measures to give the total improvement score.

A total improvement score between 0 and 100 corresponds to the degree of improvement, with higher scores corresponding to a greater degree of improvement.

APPENDIX 3 ANALYSIS PLAN FOR OPEN-LABEL, OPEN-LABEL EXTENSION AND LONG-TERM EXTENSION PERIODS ANALYSIS

Analyses specified in this section will be performed:

- 1) At the end of the open-label period, i.e. after all subjects have completed the 52-week assessment.
- 2) At the end of the open-label extension period, i.e. after all subjects have completed the 76-week assessment (Japan sites only).
- 3) At the end of the long-term extension period, i.e. after all subjects have completed the 3-year assessment and all protocol specified follow-up visits.

For sections “Background and Rationale; Study Description; Objectives; Endpoints; Sample Size and Power; Study Periods, Treatment Regimens and Populations for Analyses; Conventions” and their subsections, see [Section 1-Section 6](#) and [Section 8](#) of SAP for 24-week analysis of the double-blind study period. Any changes or modification to the analysis for the double-blind period will be explicitly presented.

The open-label analysis will include safety assessment for all safety data in the database at the time of the 52-week database lock.

The open-label extension analysis will include safety assessment for all safety data in the database at the time of the 76-week database lock.

The long-term extension analysis will include safety assessment for all safety data in the database at the time of the study final database lock.

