11.6.2 Additional Efficacy and Outcome Research Analyses

FI-2

Changes in muscle endurance measured by FI-2 scores over time in the study will be assessed using a longitudinal repeated measures mixed model. The model will include baseline FI-2 score, double-blind treatment group, randomization stratification factors disease diagnosis (DM vs. Non-DM), ILD (absent vs present), Region (Japan vs ROW), time and time by treatment interaction. The estimate of baseline mean FI-2 score, mean post-baseline FI-2 score, and adjusted mean change from baseline FI-2 score will be summarized by treatment group and visit. Treatment difference in adjusted mean changes from baseline, along with the corresponding 95% confidence intervals, will also be presented.

Myositis Response Criteria

To assess the myositis response criteria score over time during the study a longitudinal repeated mixed effects model will also be used. The mixed model will include double-blind treatment group and randomization stratification factors: disease diagnosis (DM vs. Non-DM), ILD (absent vs present), Region (Japan vs ROW), time (study days in which MRC is measured) and time by treatment interactions as fixed effects and subject as a random effect. Adjusted mean difference, SE, 95% CI for adjusted mean difference between treatment groups will be provided. The estimate of mean post-baseline MRC total improvement score will be also summarized by double-blind treatment group and visit.

[REDACTED]

[REDACTED]

[REDACTED]

[REDACTED]

[REDACTED]

[REDACTED]

post-baseline MDI, and adjusted mean change from baseline MDI score will be also be presented

[REDACTED]

[REDACTED]

[REDACTED]

[REDACTED]

[REDACTED]

[REDACTED]

[REDACTED]

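### The MRC score, ranked second among the secondary endpoints, is the only ranked secondary modelled without a baseline severity covariate; adding three baselines with time interactions is a cheap precision safeguard

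*SAP*

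**What the plan says.** SAP 7.5.1 ranks the secondary endpoints HAQ-DI, MRC, FI-2, MDAAT. Its stopping rule reads "endpoints should not be interpreted for significance if they have a rank lower than that endpoint whose null hypothesis was the first" in the sequence to be retained. P-values are still shown for all four.

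SAP 7.5.4 gives the FI-2, HAQ-DI and MDAAT models the endpoint's own baseline and a time-by-baseline term. For MRC it says "The mixed model will include treatment group and randomization stratification factors: disease diagnosis", followed by ILD, region, time and time by treatment. Appendix 3 (SAP 11.6.2) repeats this for the open-label analysis: "The mixed model will include double-blind treatment group and randomization stratification factors: disease diagnosis".

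Two other models analyse a response derived from the same six core measures, and both adjust for baseline severity:

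- Primary logistic model (SAP 7.5.2): "baseline MMT8 score, baseline MDAAT, baseline PGA and treatment group will also be included in the model".
- Cox model (SAP Table 7.1-1): "baseline MMT8 score, baseline MDAAT and baseline PGA will be included in the model".

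Other places disagree about MRC. Protocol 8.4.2.2 lists a baseline MRC score and its interaction with time. SAP Table 7.1-1 puts MRC under a model that includes the variable's baseline value, and the general text of SAP 7.1 uses the same wording for all continuous measures.

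SAP 7.1 specifies an unstructured covariance matrix, REML and Kenward-Roger degrees of freedom. Its single back-up is compound symmetry, used on non-convergence or memory problems. Subject is also named as a random effect.

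**The concern.** MRC is a sum of improvement scores, so its value at baseline is zero by construction. A baseline MRC term therefore adjusts for nothing. The three stratification factors describe disease type, lung involvement and region, not severity. As written, the MRC model makes no use of baseline severity, although Appendix 2 scores change as a percentage of each scale's range, so baseline limits how much a subject can score.

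What is at stake is precision at a point in the sequence where a missed rejection also withholds significance claims for FI-2 and MDAAT. The covariance fallback is a smaller matter. It applies to every continuous endpoint, but only if the preferred fit fails.

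**Working it through.** **1. The plan's own figure.** The plan states about 90% power for "IMACS DOI rate of 60% in the abatacept group and 33% in the placebo group", with 75 per arm, two-sided 5% and continuity correction.

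- z = [(0.27 − 1/75)·√75 − 1.96·√(2·0.465·0.535)] / √(0.60·0.40 + 0.33·0.67) = (2.223 − 1.383)/0.679 = 1.237.
- Power is 89.2%, or 90.3% by exact enumeration, so the figure reproduces. These rates serve below only to calibrate the MRC scenarios.

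**2. How baseline limits the score.** Appendix 2 fixes "Manual Muscle Testing (MMT-8): Range = 150". The largest possible MMT-8 improvement is therefore (150 − baseline)/150.

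| Baseline MMT-8 | Maximum improvement | Most points on the muscle item |
|---|---|---|
| 135 | 10% | 10 |
| 120–134 | 10.7–20% | 20 |
| 105–119 | 20.7–30% | 27.5 |
| ≤104 | ≥30.7% | 32.5 |

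MMT-8, PGA and extramuscular activity carry 32.5 + 20 + 20 = 72.5 of the 100 points. An eligible subject with MMT-8 135, PGA 2, SGA 2, HAQ-DI 0.5 and extramuscular VAS 0 can reach at most 10 + 15 + 5 + 7.5 = 37.5 without the enzyme item, and 45 with it. A severe subject (PGA 6, SGA 6, MMT-8 104, HAQ-DI 1.5, extramuscular VAS 5, ample enzyme room) can reach 100.

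**3. Precision from a Week 24-specific adjustment.** R² is assumed, because the documents give none. It comes from 108 simulated scenarios that apply the protocol's entry rule and are calibrated to DOI rates of 33% and 60%. With 128 evaluable subjects, three covariates cost a factor 1 + 3/119 in variance (128 − 5 existing terms − 3 − 1 = 119):

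SE multiplier = √[(1 − R²)(1 + 3/119)]; new power = Φ(2.80/multiplier − 1.96), starting from 80%.

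| Assumed response | R² beyond arm and strata | SE multiplier | 80% power becomes |
|---|---|---|---|
| Proportional to room, lowest | 3.2% | 0.996 | 80.3% |
| Proportional to room, median | 7.6% | 0.973 | 82.1% |
| Proportional to room, highest | 20.7% | 0.902 | 87.4% |
| Unrelated except at scale limit, highest | 1.7% | 1.004 | 79.7% |
| Unrelated except at scale limit, lowest | 0.4% | 1.011 | 79.2% |

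Break-even R² is 1 − 119/122 = 2.5%. At the full design effect, MRC power is already 92% or more without the covariates. At half that effect it is 39 to 66%, and the change adds up to 7.2 points or costs up to 0.9.

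**4. Why the time interaction is needed.** A main effect alone forces one slope on all six visits. Assume that the true slope grows linearly over visits, correlation is 0.4 + 0.6·0.7^lag and residual SD rises from 0.30 to 0.50. The generalised least squares pooled slope is then c ≈ 0.25 of the Week 24 slope. The variance removed at Week 24 falls from R² to R²·[1 − (1 − c)²] ≈ 0.44·R². The multipliers shrink to about 0.996 (R² 7.6%) and 0.966 (R² 20.7%). With equal variances c is 0.58 and more of the gain survives (0.980 and 0.922).

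**5. Fallback.** With complete data and model-based errors, compound symmetry gives a Week 24 two-sided error of 2Φ(−1.96·√(mean variance)/SD at Week 24).

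- Variance rising linearly, SD 0.30 to 0.50: mean variance 0.17, so 2Φ(−1.616) = 10.6%.
- Equal variances: 5.0%.
- Falling, SD 0.50 to 0.30: 2Φ(−2.69) = 0.7%.

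Simulated fits of plain compound symmetry with 14% dropout gave 10.7%, 5.2% and 1.1%. With empirical standard errors they gave 4.7 to 5.1%. The unstructured fit converged in all 722 six-visit and all 1,200 two-visit simulated trials.

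**The case against.** The strongest case against is that this is a choice about precision, not an error. MRC is already an improvement score, so it has no baseline of its own to adjust for. SAP 4.2 redefines the endpoint as the Week 24 score, and SAP 7.5.4 drops the protocol's baseline MRC term to match, which reads as deliberate. The sign of the effect depends on response models that the documents do not supply, and power at the design effect is already high. All of this stands, and it is why the point is an improvement and not a defect. It does not explain why MRC alone goes without the three severity baselines that the primary and Cox models use. The trade is also asymmetric: up to about 10% off the standard error against about 1% on.

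It also stands that main effects alone could lose most of the gain, as step 4 shows. Text after the MRC paragraph is redacted, so a supplementary adjusted analysis cannot be excluded. The MRC model paragraph itself is complete.

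A reader might infer that the missing covariate biases the MRC comparison or inflates its type I error. Randomisation rules that out with complete data. A chance imbalance in severity would shift the error conditionally on that imbalance, but overall it stays at 5%. A reader might also infer that the protocol's baseline MRC term yields different results from the SAP. An all-zero covariate changes no estimate.

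**Conclusion.** The point holds as a low-cost improvement. The second-ranked secondary endpoint is the only ranked secondary without a baseline severity covariate, and no visible text supplies a usable one. On assumed response models, Week 24-specific adjustment multiplies the standard error by 0.90 to 1.00 (median 0.97) if improvement scales with room, and by at most about 1.01 otherwise. That range rests on assumed baseline distributions, response models and 128 evaluable subjects.

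The fallback point is minor and conditional. Model-based errors are too small only if the unstructured fit fails and Week 24 residual variance also exceeds the visit average; below that average they are too large. A reader might conclude that the fallback is unsafe or that a ladder of alternative covariance structures is required. The documents give no visit-specific variances to support either conclusion, and convergence failure looks rare.

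**What to change.** - In SAP 7.5.4 and SAP 11.6.2, add baseline MMT-8, MDAAT extramuscular VAS and PGA to the MRC model, each with a time-by-baseline interaction, as the other three models in SAP 7.5.4 have.
- Remove the baseline MRC term from Protocol 8.4.2.2, and take MRC out of the baseline-value wording in SAP Table 7.1-1 and the general text of SAP 7.1, so that all places agree.
- In SAP 7.1, state that empirical standard errors are reported if compound symmetry is used, and that the unstructured matrix is fitted without an added random subject effect.

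The cost is wording and code before unblinding. Three slopes at each of six visits add 18 fixed-effect parameters, three of them acting at Week 24. The standard error may be up to about 1% larger if the baselines are uninformative. No subject is lost, because Appendix 2 already provides: "If one of the core measures is missing then the total score will be missing". Kenward-Roger would be given up only where the fallback is used. Empirical errors do not remove any bias that a wrong covariance causes under dropout; in the scenario simulated with compound symmetry this was about 0.02 SD.
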